2. PROTOCOL SYNOPSIS AND RESEARCH SUMMARY

2.1 Purpose

Given that many patients with HCC are not surgical candidates (for either resection or transplant), PLA techniques have become the standard non-operative approach. Non-randomized data have shown that the local control of HIGRT is comparable to that of PLA. Direct comparison of these two modalities via a randomized controlled clinical trial is the next logical step.

This research protocol will directly compare Percutaneous Local Ablation (PLA) to Hypofractionated Image-Guided Radiation Therapy (HIGRT) for patients with Hepatocellular Carcinoma (HCC) who are not surgical candidates or decline surgery while undergoing care at the Durham VA or at Duke Cancer Center.

Primary Objective

To compare change in Quality of Life (QOL), as defined by the European Organization for Research and Treatment of Cancer Quality of Life Questionnaire Core-30 (EORTC C-30), from baseline to 1 month post treatment in patients receiving PLA vs HIGRT.

Secondary Objectives

1. To estimate the difference in change in QOL in patients receiving PLA vs HIGRT, as measured EORTC C-30, from baseline to 3 months post-treatment
2. To estimate the difference in change in QOL in patients receiving PLA vs HIGRT, as measured EORTC C-30, from baseline to 6 months post-treatment
3. To estimate the difference in change in QOL in patients receiving PLA vs HIGRT, as measured by FACT-Hep, from baseline to 1 month, baseline to 3 months and baseline to 6 months post-treatment
4. To assess for grade ≥ 2 acute toxicity within 90 days of treatment initiation
5. To estimate the total healthcare system cost associated with PLA vs HIGRT from time of intervention through 90 days post treatment

Exploratory Objectives

1. To assess for grade 3+ late toxicity (>90 days post ablative therapy or radiation therapy)
2. To evaluate local control at the treated site within the liver
3. To evaluate distant liver recurrence (intrahepatic lesions other than treated lesion)
4. To evaluate median progression free survival (PFS)
5. To evaluate median overall survival (OS)

Hypotheses

For the primary endpoint of change in QOL at 1 month post treatment versus baseline, HIGRT will have significantly better patient reported global QOL than PLA.

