3.2 Percutaneous Localized Ablation (Microwave Ablation, control arm)

Microwave Ablation (MWA) is a form of percutaneous localized ablation using thermal ablation techniques to treat cancer via direct coagulative necrosis. Microwaves can generate high temperatures in a short period of time; MWA has the potential to improve treatment efficacy over radiofrequency ablation as it can be used to treat larger lesions and has less susceptibility to heat-sink due to vessel proximity. MWA uses electromagnetic waves (300 MHz to 300 GHz) to produce oscillation of polar molecules within tissue; this generates tissue necrosis through frictional heating. For HCC, one or more microwave antennae are inserted into the liver, usually under the guidance of ultrasonography or computed tomography (CT). Frequency and length of treatment is determined on a case by case basis depending on tumor size and proximity to vessels or other organs at risk. PLA is administered as a single treatment.

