5. *To estimate the total healthcare system cost associated with PLA vs HIGRT from time of intervention through 90 days post treatment.* Costs will be estimated based on national averages for billable charges for all codes associated with PLA vs HIGRT throughout the course of treatment and the post-treatment follow up. This includes costs associated with any hospitalizations related to either procedure. Total costs per arm will be described with boxplots. Arm differences in the health care cost will be estimated using the statistical method best suited to the observed distribution of cost in these data (for example, a single distribution generalized linear model specifying, perhaps, a Gamma distribution).

Exploratory Endpoints:

1. *To assess for late toxicity (>90 days post PLA or HIGRT).* Late toxicity will be defined as any Grade 3+ toxicity occurring after the completion of the treatment regimen up to 6 months post-PLA or HIGRT. The proportion of patients experiencing any type of late toxicity will be estimated with an exact 95% confidence interval, by arm.
2. *To evaluate local control at the treated site within the liver.* Time to local failure will be defined as the length of time from enrollment to local failure at the site of treated disease within the liver (within the PTV). Intrahepatic sites distinct from treated lesions and distant failures will be ignored and deaths will be censored. The distribution of time to local failure will be estimated with the Kaplan-Meier method, by arm.
3. *To estimate distant liver recurrence (intrahepatic lesions other than treated lesion).* Time to distant liver recurrence will be defined as the length of time from date of enrollment to intrahepatic failure not within the site of treated disease; distant failures will be ignored and deaths will be censored. The distribution of time to distant failure will be estimated with the Kaplan-Meier method, by arm.
4. *To estimate median progression-free survival (PFS).* PFS will be defined as the length of time from enrollment to local or distant failure or death, whichever comes first. The distribution of PFS will be estimated with the Kaplan-Meier method, by arm.
5. *To estimate median overall survival (OS).* Overall survival (OS) will be defined as the length of time from enrollment to death due to any cause. The distribution of OS will be estimated with the Kaplan-Meier method, by arm.

5. STUDY SCHEMA (Pooled patients from Durham VAMC and Duke)

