8.1 Type, Classification, Location, and Short Description

Therapy is high dose image guided radiotherapy (HIGRT) delivered in 5-10 fractions.

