In accordance with the HIPAA and the Privacy Act, for any coded or identifiable data or specimens released from the Durham VAMC (with the exception of Limited Data Sets), an Accounting of Disclosure (AOD) will be

maintained (e.g., in a database or spreadsheet) that includes the participant's name, date of the disclosure, description of the nature of the Individually Identifiable Information (III) disclosed, purpose of each disclosure, and the name and address of the person/agency to whom the disclosure was made.

Section 17 subheadings 1 through 18 data security requirements is applicable to the study team at the Durham VAMC

1. Lists of Data Reviewed and/or Collected for Screening/Recruitment and Conduction of Study:

The Personal Health Information that will be obtained, used, and/or shared for this study includes:

Identifier(s)	Source(s) of Health Information
 Names	 Medical history & physical exam information
 All geographic subdivisions smaller than a State, including street address, city, county, precinct, and zip code. Describe:	 Photographs, videotapes, audiotapes, or digital or other images
 All elements of dates (except year) for dates directly related to an individual, including birth date, admission date, discharge date, visit or treatment dates, etc.; and all ages over 89, Describe: DOB, initial imaging dates, dates of treatment, dates of hospitalizations (if any) and FU visit/imaging dates and dates of questionnaire completion will be recorded	 Biologic specimens (e.g., blood, tissue, urine, saliva). Describe:
 Telephone numbers	 Progress notes
 Fax numbers	 Diagnostic / Laboratory test results
 Electronic mail addresses	 Operative reports
 Social Security Numbers (SSN will not be collected for subjects treated at Duke Cancer Center)	 Imaging (x-ray, CT, MRI, etc.)
 Medical record numbers	 Discharge summaries
 Health plan beneficiary numbers	 Survey / Questionnaire responses

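### Secondary Endpoint 5 is named healthcare system cost but is valued at billable charges, so the planned arm contrast is a difference in charges

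*Combined protocol and SAP*

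**What the plan says.** Section 2.1 lists as Secondary Objective 5: "To estimate the total healthcare system cost associated with PLA vs HIGRT from time of intervention through 90 days post treatment". Section 4 repeats the objective as Secondary Endpoint 5 and adds the method.

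- **Valuation:** "Costs will be estimated based on national averages for billable charges for all codes associated with PLA vs HIGRT", covering care "throughout the course of treatment and the post-treatment follow up".
- **Hospital stays:** "This includes costs associated with any hospitalizations related to either procedure".
- **Analysis:** boxplots of total cost per arm, and "Arm differences in the health care cost will be estimated using the statistical method best suited to the observed distribution of cost". A Gamma generalized linear model is offered as one example.

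No section names the source of the national averages, the price year, a payment schedule or a cost-to-charge ratio.

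The two arms consist of different services. Section 8.1 states: "Therapy is high dose image guided radiotherapy (HIGRT) delivered in 5-10 fractions". Sections 8.4 and 8.9 add CT-based planning and image guidance before each delivery. For the control arm, Section 3.2 states: "PLA is administered as a single treatment". Section 9.1 adds moderate sedation or general anaesthesia.

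**The concern.** The quantity named in the objective and the quantity measured are not the same. A charge is an amount billed, whereas the cost to a healthcare system is what it spends. The plan moves from one to the other without a conversion and without saying that the two may be treated as equal or proportional.

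If every service had the same cost-to-charge ratio, the substitution would only rescale both arms. The arms use such different services that a common ratio cannot be taken for granted. Any difference in ratio between radiotherapy planning and delivery on one side, and an interventional procedure with sedation or anaesthesia on the other, goes straight into the arm contrast.

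What is at stake is the interpretation of a named secondary objective. A reader of the results would take a figure labelled as healthcare system cost to show how much more or less one treatment costs, and the planned measure does not establish that.

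**Working it through.** **Is there a figure to reproduce?** No. The documents give no unit price, expected cost, cost SD or power statement for this endpoint. The sample-size calculation in Sections 2.2.3 and 4 concerns change in quality of life only. Every price and ratio below is therefore an assumption that shows how the measure behaves; none is an estimate for this trial.

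**Step 1: link charges to costs.** For service j, let B_j be the mean charge per patient and r_j the cost-to-charge ratio. Within an arm:

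- mean charge B = ΣB_j
- mean cost C = Σ r_j B_j = r × B, where r = Σ r_j B_j / ΣB_j is the charge-weighted ratio for that arm.

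With H for HIGRT and P for PLA:

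- cost ratio: C_H / C_P = (B_H / B_P) × (r_H / r_P)
- cost difference: C_H − C_P = r_H B_H − r_P B_P

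The plan as written estimates a contrast of B_H and B_P. The objective asks for a contrast of C_H and C_P.

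**Step 2: equal ratios.** Suppose costs are 20 (HIGRT) and 15 (PLA) units and charges are three times cost in both arms. Charges are then 60 and 45. The ratio is 60/45 = 20/15 = 1.33 on either scale. The absolute difference is 15 in charges and 5 in cost. A common ratio therefore preserves direction and relative size but not absolute size. The plan does not say whether the arm contrast will be a difference or a ratio.

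**Step 3: unequal ratios, with charges held at 60 and 45.**

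| r_H | r_P | r_H / r_P | Cost, HIGRT | Cost, PLA | Cost ratio |
|---|---|---|---|---|---|
| 0.25 | 0.40 | 0.625 | 60 × 0.25 = 15 | 45 × 0.40 = 18 | 0.83 |
| 0.30 | 0.40 | 0.75 | 60 × 0.30 = 18 | 45 × 0.40 = 18 | 1.00 |
| 1/3 | 1/3 | 1.00 | 20 | 15 | 1.33 |
| 0.40 | 0.25 | 1.60 | 60 × 0.40 = 24 | 45 × 0.25 = 11.25 | 2.13 |

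**Step 4: threshold for a change of direction.** If charges are higher on HIGRT, the direction reverses when r_H / r_P < 1 / (B_H / B_P). For charge ratios of 1.1, 1.25, 1.33, 1.5 and 2.0, the thresholds are 0.91, 0.80, 0.75, 0.67 and 0.50. If charges are lower on HIGRT, with ratios of 0.9, 0.8 and 0.7, reversal needs r_H / r_P above 1.11, 1.25 and 1.43. The further apart the charges, the larger the imbalance in ratios that is needed.

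**Step 5: does national averaging help?** It gives each code one price at both sites, so price differences between the Durham VA and Duke drop out. It leaves r_j different from service to service, which is the part that does not cancel between arms.

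**The case against.** The strongest reply is that the plan's term is undefined and may be meant as a national fee or payment schedule. If so, the method already matches the objective and only the wording is loose. That is possible, but nothing in the document says it, and the literal text is a charge. Stating the source would settle it.

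A second reply is that unequal ratios between services are not shown anywhere in the document. That is correct. The point made here is narrower: proportionality is an assumption, the plan does not state it, and the arms are different enough that it needs support. National averaging is also a sound choice for removing site price differences and should be kept.

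A third reply is that this is the last of five secondary objectives in a phase II trial, with estimation only and no decision rule. This stands, and it limits the consequence.

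Three stronger readings are tempting but not supported:

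- **That the arm difference will have the wrong sign.** The document holds no charge, cost or ratio data. Reversal is arithmetically possible past the thresholds above, and nothing shows that they are crossed.
- **That only stays judged related are counted, with a judgement biased by knowledge of the arm.** The text says that related stays are included. Related-only is a natural reading, but the word is not there. No assessor or rule for stays is described in Secondary Endpoint 5, although Section 12.1 gives a five-level attribution scale for adverse events. Biased attribution is conceivable but not shown.
- **That all-cause stays must be the main measure.** The objective is cost associated with the two treatments, so restricting to related care does not contradict it. Section 7.1.5 places no limit on further HCC therapy after treatment completion, so an all-cause total could also bring in the cost of later treatment. Nor can complete data be presumed: the list of hospitalisation dates and billing records in Section 17 is stated to apply to the Durham VAMC team.

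**Conclusion.** The mismatch holds on the text: the objective is cost, the measure is charges, and no conversion or payment schedule is given. The planned contrast is a charge difference. It is proportional to a cost difference only under a common cost-to-charge ratio across a radiotherapy course of several fractions and a single ablation procedure.

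The size of the distortion cannot be determined from the document. On the assumed charge ratio of 1.33, the cost ratio would be 1.33 with equal ratios, and would run from 0.83 to 2.13 as r_H / r_P goes from 0.625 to 1.60, with reversal only below 0.75. These values show the mechanism and are not a forecast.

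The consequence is confined to Secondary Endpoint 5. The primary analysis and the sample size are unaffected. It is still worth correcting, because the remedy is cheap and the endpoint otherwise does not measure what its objective names.

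**What to change.** In Secondary Endpoint 5 of Section 4, value each code at the national average payment (allowed amount) instead of the billable charge. Name one price source and one price year, and apply them to both arms and both sites. If the present wording was already meant as a payment schedule, say so and name it.

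If charges are kept, rename the objective in Section 2.1 and the endpoint in Section 4 as billable charges, and do not interpret the result as cost.

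Optionally, where the data are available at both sites, report all-cause hospitalisations within 90 days as a sensitivity analysis. Keep the total based on related hospitalisations as the main measure, because that fits the objective as worded. Availability at Duke would need to be confirmed first.

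The main change costs a revised paragraph and a different price list. It needs no new patient data, visits or patients. The downside is that payment-based figures may look less favourable than charge-based ones.

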1. *To estimate the change in QOL in patients receiving PLA vs HIGRT, as measured by EORTC C-30, from baseline to 3 months post-treatment.* The mean difference between arms in change from baseline to 3 months in QLC-C30 will be estimated with their 95% confidence intervals [CI]. To calculate these CI's, the mean arm difference in QOL and its standard error will be estimated from a general linear model in which change in QOL is regressed on arm, controlling for the baseline value of QOL and the Child Pugh score.
2. *To estimate the change in QOL in patients receiving PLA vs HIGRT, as measured by EORTC C-30, from baseline to 6 months post-treatment.* The mean difference between arms in change from baseline to 6 months in QLC-C30 will be estimated with their 95% confidence intervals [CI]. To calculate these CI's, the mean arm difference in QOL and its standard error will be estimated from a general linear model in which change in QOL is regressed on arm, controlling for the baseline value of QOL and the Child Pugh score.

3. *To estimate the change in QOL as measured by FACT-Hep in patients receiving PLA vs HIGRT.* Change in FACT-Hep score from baseline to 1 month, baseline to 3 months and baseline to 6 months will be calculated for each patient, and the mean arm difference in change will be estimated with its 95% CI. The CI will be estimated as described for Secondary Objective 1.
4. *To estimate grade ≥ 2 acute toxicity within 90 days of treatment initiation.* CTCAE version 4 will be used for all toxicity assessments. The acute toxicity rate will be defined as any grade 2+ toxicity occurring during treatment through 90 days post-PLA or post-HIGRT. The acute toxicity rate with its exact 95% confidence interval will be estimated within each arm. The arm difference in acute toxicity rate will be estimated with its 95% CI. We will also estimate the rate of hospitalization due to treatment complications with its 95% CI and the proportion of patients requiring treatment breaks longer than 7 days from HIGRT, with its 95% CI.

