7.1.3 Safety Considerations

An **interim analysis** will be performed after the first 40 patients have been followed for 90 days after completion of study therapy. Accrual will not be halted during this analysis. All treatment-related grade 4-5 AEs occurring within 90 days of treatment will be tabulated and reviewed. If > 20% of patients experience grade 4-5 AEs attributable to treatment, a decision will be made to either: 1) halt the trial and all further accrual, 2) amend the protocol for more aggressive dose modification and/or 3) institute additional clinical monitoring.

Anticipated risks associated with PLA include:

- pain (muscle aches or spasm may occur for 3-5 days)
- nausea/vomiting
- infection
- fever
- liver damage
- blood vessel/nerve damage; this could require admission to hospital

Rare but very serious PLA risks include:

- liver damage which could cause liver failure
- bleeding from the liver which could be life threatening
- liver abscess (serious infection)

Anticipated risks associated with HIGRT include:

- fatigue
- pain
- nausea/vomiting

- **Rare but very serious HIGRT risks include:**
- liver damage which could cause liver failure
- rib fracture
- chest wall pain

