7.4 Definition of Evaluable Subjects, On Study, and End of Study

Patient are “on study” during the intervention time period (either ablation or HIGRT) and the 6-month follow up while additional survey data is being collected. End of study is defined as 180 days post-therapy (+/- 30 days) at the time of the last follow up survey. We will continue to collect patient data from the EHR for 5 years after study enrollment or until death. For the purposes of the primary endpoint of QOL, a patient who has received either ablation or HIGRT and completed at least the baseline and month 1 follow up QOL surveys will be analyzed.

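### The late-toxicity definition starts at completion of treatment, not after day 90, so grade 3+ events in the first 90 days count as late as well as acute

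*Combined protocol and SAP*

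**What the plan says.** Late toxicity is described in three places. Exploratory Objective 1 (section 2.1) asks about "grade 3+ late toxicity (>90 days post ablative therapy or radiation therapy". The heading of Exploratory Endpoint 1 (section 4) repeats the bound: "late toxicity (>90 days post PLA or HIGRT". The sentence that then defines the endpoint covers "any Grade 3+ toxicity occurring after the completion of the treatment regimen up to 6 months post-PLA or HIGRT". The analysis is a proportion of patients: "late toxicity will be estimated with an exact 95% confidence interval, by arm".

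Acute toxicity is Secondary Endpoint 4 in the same section, defined as "any grade 2+ toxicity occurring during treatment through 90 days post-PLA or post-HIGRT". Because it takes grade 2 and above, it includes every grade 3+ event in that period. Its heading, like Secondary Objective 4 in section 2.1, uses a different clock: "acute toxicity within 90 days of treatment initiation".

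Section 7.4 fixes the length of on-study follow-up: "End of study is defined as 180 days post-therapy (+/- 30 days".

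**The concern.** The defining sentence does not leave the start of the late window open. It names completion of the regimen, which conflicts with the 90-day bound in its own heading and in the objective. An analyst who programs the definition will include the first 90 days. One who follows the heading will not. Both could cite the protocol and report different rates.

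Under the literal rule, early grade 3+ events would be reported twice, once as acute and once as late, and the late rate would no longer answer its objective. Results are given by arm, so a difference between PLA and HIGRT in early severe toxicity would also appear as a difference in late toxicity. Section 12.1 requires adverse events to be recorded from consent to the end of study, so the early events will be in the dataset and available to be counted.

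**Working it through.** The plan states no rate, sample size or power for late toxicity, so there is no figure of its own to reproduce. The check compares the windows and then illustrates the effect with assumed rates.

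**1. Windows, in days after completion of treatment**

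| Source | Window |
|---|---|
| Late: Exploratory Objective 1 and endpoint heading | after day 90 |
| Late: defining sentence | day 0 to 6 months (about day 180) |
| Acute: defining sentence, Secondary Endpoint 4 | during treatment through day 90 |

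The two defining sentences overlap from day 0 to day 90 in both arms. Events during the HIGRT course itself are acute only.

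**2. Share of the written late window that is also acute**

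- End at day 180: 90/180 = 50%.
- End at day 210 or 150 (the 30-day tolerance in section 7.4): 90/210 = 43%, 90/150 = 60%.

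**3. Does the other acute clock remove the overlap?** The acute heading counts 90 days from initiation. PLA is a single treatment (section 3.2), so its overlap stays at 90 days. HIGRT takes 2 or 3 weeks (section 8.6), so its overlap is 90 − 14 = 76 or 90 − 21 = 69 days. It is never zero.

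**4. Direction.** Events after day 90 are a subset of the events that the written definition counts. The written rate is therefore at least the intended rate, whatever the true rates are.

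**5. Size under assumed rates.** Let e be the proportion of patients with a grade 3+ event in days 0–90 and l the proportion with one after day 90. The written rate lies between max(e, l), if the same patients have both, and e + l, if different patients do. If the two are independent it is 1 − (1 − e)(1 − l). Expected counts use 45 patients per arm (90 randomized equally).

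| Assumed e / l | Intended late rate | Written late rate (independent) | Expected patients, written vs intended |
|---|---|---|---|
| 2% / 2% | 2% | 2–4% (4.0%) | 0.9–1.8 vs 0.9 |
| 5% / 2% | 2% | 5–7% (6.9%) | 2.3–3.2 vs 0.9 |
| 10% / 3% | 3% | 10–13% (12.7%) | 4.5–5.9 vs 1.4 |

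For example, in the second row 45 × 0.05 = 2.25 and 45 × 0.07 = 3.15, against 45 × 0.02 = 0.9.

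**6. Precision.** Exact (Clopper-Pearson) 95% intervals are 0.1–11.8% for 1/45 (2.2%), 1.4–18.3% for 3/45 (6.7%) and 5.1–26.8% for 6/45 (13.3%). They overlap. The harm is that the wrong events are labelled late, not that a statistical conclusion is reversed.

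**The case against.** The strongest reply is that the endpoint should be read as one item. The heading supplies the lower bound, and the next sentence adds the grade and the upper limit. Two of the three statements say more than 90 days, so the intent is fairly clear. That stands as evidence of intent, and a careful analyst might read it that way. It does not remove the conflict, because the sentence gives its own starting point and nothing excludes acute events from the late count.

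It is also fair that nothing decisive depends on this endpoint. It is exploratory and has no planned test. The interim safety rule in section 7.1.3 has its own definition, and no total adds acute and late rates together. The scenarios rest on assumed rates, and section 7.1.3 presents the most serious harms as uncommon ("Rare but very serious PLA risks include"), so the lower rows may be the more plausible. The 43–60% range applies the visit tolerance to a window that the endpoint ends at 6 months, so 50% is the main figure. Forty-five per arm is an upper figure, since patients who receive neither treatment are withdrawn. All of this limits the importance of the point but leaves the contradiction in place.

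A last objection is that the remedy follows the heading for late toxicity but the definition for acute toxicity. The reason is that the windows then meet. If acute toxicity ran 90 days from initiation and late toxicity began 90 days after completion, HIGRT patients would have an unclassified gap of 14 or 21 days.

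**Conclusion.** The definition is wrong as written. Taken literally, it counts grade 3+ events from completion through day 90 as late, contrary to the objective and the endpoint heading, and half of its 180-day window duplicates the acute window. The direction of the error is certain: the reported late rate equals or exceeds the intended one. Its size is not known, because the documents give no event rates. Across the assumed cases the excess runs from nothing (2%/2%, same patients) to 10 percentage points (13% instead of 3%).

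The point concerns a descriptive exploratory endpoint and should be corrected before analysis. The mismatch in the acute wording is minor. It affects HIGRT only, by roughly the length of the course, and its effect on the rate was not quantified. It is probably small if toxicity occurs early.

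**What to change.** In section 4, Exploratory Endpoint 1, define late toxicity as any grade 3 or higher toxicity with onset more than 90 days after completion of PLA or HIGRT, up to 6 months after treatment. Keep the acute definition in Secondary Endpoint 4, and change its heading and Secondary Objective 4 (section 2.1) so that they use the same clock. The two windows then meet without overlap or gap.

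Confirm that the adverse event form records onset date. Section 12.1 requires events to be recorded but does not say so, and the acute endpoint and the interim safety review need event timing in any case.

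The cost is one sentence and two small wording edits, with no change to treatment, visits or sample size. The late rate will rest on fewer events and on about 90 days of follow-up (180 − 90), or 60 to 120 days if the last visit falls at day 150 or day 210.
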